### **15.3 Analysis of Safety**

Descriptive statistics and appropriate tests will be used to summarize and compare the safety parameters between treatment groups. All safety analyses will be performed on the safety population. Treatment group comparisons may assess the significance of the difference between treatment and control groups.

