8.4.1. Primary Endpoints

The primary analysis compares the components of the primary composite endpoint hierarchically using the Finkelstein-Schoenfeld Method. Each patient is compared to all other patients with respect to each of the following endpoints at 30 days:

- CV death
- HF hospitalization
- Urgent ED/Clinic visit for worsening heart failure (defined as IV diuretics, augmentation of or new administration of metolazone)
- Change in NT-proBNP from baseline at Day 7.

Each endpoint will be descriptively presented as well.

Incidence of Adverse Events, Adverse Events of Special Interest, and Serious Adverse Events will be described in each group.

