### **4. SAMPLE SIZE**

Fifty-one (51) subjects will be included and randomly assigned in a 2 to 1 ratio to receive Furoscix (n=34) or continued medical therapy (n=17) in the home setting with 30 days of follow-up. Given the exploratory nature of this study, no formal power analysis of sample size was conducted.

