## 10. ENDPOINTS

### 10.1 Primary Endpoints

- Improvement in a composite/combined morbidity/mortality endpoint at 30 days using the Finkelstein Schoenfeld method.
  - CV death
  - HF hospitalization
  - Urgent ED/Clinic visit for worsening heart failure (defined as IV diuretics, augmentation of or new administration of metolazone)
  - Percent change in NT-proBNP from baseline at Day 7
- Incidence of Adverse Events, Adverse Events of Special Interest, and Serious Adverse Events

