- Changes from baseline in health-related quality of life, measured by the KCCQ-12 Short Form Overall Summary Score, across follow-up timepoints will be analyzed using a GEE model with treatment arm, and timepoint and treatment by timepoint interaction as a fixed effect, and the baseline value of the KCCQ-12 Overall Summary Score as covariates. An unstructured covariance matrix structure will be used to model the within subject errors.
- Changes from baseline in serum creatinine across follow-up timepoints will be analyzed using GEE model with treatment arm, and timepoint and treatment by timepoint interaction as a fixed effect, and the baseline value of serum creatinine as covariates. An unstructured covariance matrix structure will be used to model the within subject errors.
- Changes from baseline in body weight across follow-up timepoints will be analyzed using a GEE model with treatment arm, and timepoint and treatment by timepoint interaction as a fixed effect, and the baseline value of body weight as covariates. An unstructured covariance matrix structure will be used to model the within subject errors.
- Changes from baseline in Six-Minute Walk Distance (6MWD) across follow-up timepoints will be analyzed using a GEE model with treatment arm, and timepoint and treatment by timepoint interaction as a fixed effect, and the baseline value of 6MWD as covariates. An unstructured covariance matrix structure will be used to model the within subject errors.
- Changes from baseline in the ReDS percent lung fluid measurement across follow-up time points will be analyzed using a GEE model with treatment arm, and timepoint and treatment by timepoint interaction as a fixed effect, and baseline value as covariates.

An unstructured covariance matrix structure will be used to model the within subject errors.

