#### **15.3.3 Adverse Events of Special Interest**

AESI will be listed, sorted by treatment group, subject identification number, and onset date. The number and percentage of subjects with an adverse event of special interest by MedDRA™ SOC and PT will be displayed by treatment group.

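### For AE, SAE and AESI incidence, a primary endpoint, SAP 15.3 offers an unnamed and partly optional significance test but no risk difference or confidence interval; at 34 vs 17, non-significance would say very little about safety

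*SAP*

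**What the plan says.** SAP 10.1 lists "Incidence of Adverse Events, Adverse Events of Special Interest, and Serious Adverse Events" among the primary endpoints, and safety is part of the primary objective (SAP 6.1). For the analysis, SAP 15.3 says "Descriptive statistics and appropriate tests will be used to summarize and compare the safety parameters between treatment groups" and then "Treatment group comparisons may assess the significance of the difference between treatment and control groups". The first sentence commits to tests and the second makes them optional. Neither names a test. SAP 15 sets a two-sided 0.05 level with no multiplicity adjustment.

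The subsections add description only. SAP 15.3.1 and 15.3.2 give numbers and percentages of subjects, and listings. SAP 15.3.3 tabulates "The number and percentage of subjects with an adverse event of special interest by" MedDRA class and term. Protocol 8.4.1 is purely descriptive: "Incidence of Adverse Events, Adverse Events of Special Interest, and Serious Adverse Events will be described in each group". SAP 15 states that the SAP prevails over the protocol.

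Elsewhere the SAP does plan estimates. Section 15.2.1.1 specifies a difference in proportions with a 95% CI for CV death, and the same approach for HF hospitalization and urgent visits. It also specifies an LS-mean treatment difference with a 95% CI for NT-proBNP. For creatinine, SAP 15.2.2 says only "Changes from baseline in serum creatinine across follow-up timepoints will be analyzed using GEE model with treatment arm" and the remaining model terms; no interval is named. SAP 4 gives 34 and 17 subjects and says that "no formal power analysis of sample size was conducted".

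**The concern.** The study is a pilot meant to inform a pivotal trial. For safety, what it can usefully pass on is how much excess risk the data still allow, which is the upper limit of an interval. A significance test with 17 controls does not supply that. It returns p>0.05 for most excesses of clinical interest, and the p-value alone does not show whether the data exclude a large harm or merely fail to detect one. Leaving the test unnamed and partly optional also leaves open which safety p-values will appear. The SAP authors used the more informative format for the event components of the composite but did not carry it over to the safety endpoint.

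**Working it through.** **Inputs.** Arm sizes 34 and 17 (SAP 4); two-sided 0.05 (SAP 15). The documents state no event rate, harm margin or power, so the rates below are assumptions over a range. No dropout is assumed, and controls are taken to be in the safety set (see the fix).

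**The plan's own figure.** 51 × 2/3 = 34 and 51 × 1/3 = 17, so the split checks. There is no power figure to reproduce.

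**Power.** Sum over all tables (a of 34, b of 17) of Bin(a; 34, pT) × Bin(b; 17, pC), counting those with p ≤ 0.05 and a/34 > b/17. SAP 15.3 names no test, so both Fisher's exact and uncorrected chi-square are shown.

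| Control vs Furoscix (assumed) | Fisher | Chi-square |
|---|---|---|
| 5% vs 15% | 6% | 10% |
| 5% vs 20% | 18% | 25% |
| 10% vs 20% | 8% | 11% |
| 10% vs 30% | 30% | 33% |
| 20% vs 40% | 22% | 28% |
| 30% vs 50% | 22% | 29% |

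For 80% power by Fisher, the Furoscix rate must reach 40% against 5%, 49.5% against 10%, 61.6% against 20%, or 72.2% against 30%. That is an excess of 35 to 42 points.

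**Where the test turns significant.** With 0/17 control events it takes 8/34 (23.5%). For 7/34 vs 0/17, conditional on 7 events in total, the probability that all fall on Furoscix is 0.0465. The tables at least as improbable on the other side (0, 1 or 2 on Furoscix) add 0.0002 + 0.0036 + 0.0300. The sum is p=0.080. With 1/17 it takes 11/34 (32%); 10/34 gives p=0.075.

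**What an interval would show.** Newcombe's interval combines the Wilson limits (l, u) of each arm:

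- lower = d - √[(p1 - l1)² + (u0 - p0)²]
- upper = d + √[(u1 - p1)² + (p0 - l0)²]

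For 7/34 vs 0/17: d = 0.2059, Wilson limits 0.1035 to 0.3680 and 0 to 0.1843.

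- lower = 0.2059 - √(0.1024² + 0.1843²) = 0.2059 - 0.2108 ≈ -0.005
- upper = 0.2059 + (0.3680 - 0.2059) = 0.368

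| Illustrative counts | Difference, points (95% CI) | Fisher p |
|---|---|---|
| 7/34 vs 0/17 | +20.6 (-0.5 to +36.8) | 0.080 |
| 10/34 vs 2/17 | +17.6 (-8.2 to +36.4) | 0.29 |
| 3/34 vs 0/17 | +8.8 (-10.5 to +23.0) | 0.54 |
| 4/34 vs 1/17 | +5.9 (-16.4 to +21.5) | 0.65 |
| 0/34 vs 0/17 | 0.0 (-18.4 to +10.2) | 1.0 |

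All five are non-significant. Four leave excesses above 20 points open; the fifth caps the excess near 10 points. The interval separates these cases far better than the p-value does.

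**The case against.** The strongest reply is that the safety plan is essentially descriptive. The study is an unpowered pilot, Protocol 8.4.1 only describes incidence by arm, and SAP 15.3 says comparisons may assess significance, not that they must. Counts and percentages by arm are firmly planned, they are comparative output, and anyone can derive a difference and interval from them. This stands in part, and it limits the point.

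A reader might go further and infer three things that the documents do not support:

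- **That the plan will read non-significance as safety.** No sentence in either document says so.
- **That a p-value is the only comparative safety output, or that a non-significant result would carry no information.** By-arm incidences are planned, and laboratory shift tables by treatment group are too. Non-significance does argue against excesses of roughly 35 to 42 points or more, and 0/34 alone bounds the Furoscix rate at 1 - 0.05^(1/34) = 8.4% one-sided, or 1 - 0.025^(1/34) = 10.3% two-sided.
- **That no safety-relevant outcome gets an interval.** CV death and HF hospitalization do, as efficacy components on the ITT and PP sets.

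Nor can a power figure for creatinine be taken from a simple two-sample t-test. The planned model is a baseline-adjusted repeated-measures GEE, and the documents give no correlations from which to compute its power.

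What the reply does not remove is that one sentence of SAP 15.3 commits to tests, the SAP prevails over the protocol, and an interval that readers could derive is not one that the plan specifies.

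**Conclusion.** The point holds as a cheap and worthwhile improvement, not as a fatal flaw. For AE, SAE and AESI incidence the plan mentions a significance test and no risk difference or confidence interval. Across the assumed control rates of 5% to 30%, Fisher's test at 34 vs 17 misses excesses of 10 to 20 points in about 70% to 94% of trials; chi-square is only slightly better, at about 67% to 90%. A non-significant result would therefore say very little about comparative safety. This rests on the assumed rates, on full arms of 34 and 17, and on controls being counted in the safety population.

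That last condition is not secure. SAP 14 and Protocol 8.2 restrict the safety population to randomized subjects given at least one dose of Investigational Product, while Protocol 6.2.2 excludes controls from study product administration. Read literally, there is no control arm for any safety comparison, which conflicts with the between-group comparison in SAP 15.3.

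**What to change.** 1. **First, reconcile the safety population** in SAP 14 and Protocol 8.2 with the between-arm comparison in SAP 15.3, so that it is clear whether and how controls are included.
2. **In SAP 15.3**, specify the risk difference (Furoscix minus control) with a two-sided 95% Newcombe or Miettinen-Nurminen CI for any AE, any SAE, each AESI and AEs leading to study discontinuation. Study discontinuation is the usable category: controls receive no study product, so AEs leading to its discontinuation may be zero in that arm by design.
3. Make this the main between-arm safety comparison. If p-values are kept, name the test and label them descriptive. State that a non-significant difference is not evidence of comparable safety.
4. **In SAP 15.2.2**, report the LS-mean treatment difference in creatinine with its 95% CI, as 15.2.1.1 already does for NT-proBNP.

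The cost is SAP wording and one extra column per safety table; no new data are needed. The downside is that wide intervals are shown openly.

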#### **15.3.1 Adverse Events**

Adverse events will be mapped to the Medical Dictionary for Regulatory Activities (MedDRA™) dictionary, version 23.1 . Adverse events (AE) will be summarized using number and percentage of subjects within each category of each variable overall for any AE, TEAE, serious AE, treatment related AE, AE resulting in death, AE leading to treatment discontinuation, and AE leading to study discontinuation. The incidence rates of AE will also be presented for severity, outcome, causality, and seriousness. For subjects with more than one AE within a given variable (e.g., severity), the event with the highest level of severity, outcome or causality, seriousness, respectively, will be reported. Incidence rates will also be presented for the System Organ Class (SOC) and Preferred Term (PT) of each AE. Data presented will include the number of subjects and percentage of subjects, the SOC and PT for each AE. All AEs will be presented in a listing for the Safety Population.

#### **15.3.2 Serious and Treatment Emergent Adverse Events**

SAEs and TEAEs will be listed, sorted by treatment group, subject identification, and onset date. In addition, the incidence (number and percentage of subjects) with SAEs by MedDRA SOC and PT will be displayed by treatment group.

#### **15.3.3 Adverse Events of Special Interest**

AESI will be listed, sorted by treatment group, subject identification number, and onset date. The number and percentage of subjects with an adverse event of special interest by MedDRA™ SOC and PT will be displayed by treatment group.

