6.1.3. Assessment of Adverse Events of Special Interest

Subjects will have blood drawn at each clinic visit to monitor safety parameters. Subjects will specifically be monitored for the following adverse events:

- Worsening kidney function, defined as increase of ≥ 0.5 mg/dl in serum creatinine
- Hyperkalemia, defined as $K > 5.5$ mEq/L
- Hypokalemia, defined as $K < 3.5$ mEq/L
- Hypomagnesemia, defined as $Mg < 1.5$ mg/dL

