7.1. Definition of an Adverse Event (AE)

An Adverse Event (AE) is any untoward medical occurrence associated with the use of an Investigational Product (IP) in humans, whether considered related to the IP. An adverse event (also referred to as an adverse experience) can therefore be any unfavorable and unintended sign (including an abnormal laboratory finding), symptom, or disease temporally associated with the use of an Investigational Product (IP) and does not imply any judgment about causality. An adverse event can arise with any use of the IP (e.g., off-label use, use in combination with another drug) and with any route of administration, formulation, or dose, including an overdose.

A “pre-existing” condition is one that is present prior to IP administration and is reported as part of the Subject’s medical history. Pre-existing conditions should be reported as AEs only if the frequency, intensity, or character of the pre-existing condition worsens during the study.

Laboratory or functional test abnormalities generally are not considered AEs unless they are associated with clinical signs or symptoms or require medical intervention. A laboratory abnormality (e.g. a clinically significant change detected on clinical chemistry, hematology, urinalysis) or functional test abnormality (e.g. a clinically significant change detected on ECG, pulse oximetry, or spirometry) that is independent from a known underlying medical condition and that requires medical or surgical intervention, or leads to IP interruption or discontinuation, must be considered an AE.

All AEs judged to be clinically significant, including clinically significant laboratory results, ECG and functional test abnormalities, will be followed until resolution or return to baseline or until no further improvement is expected.

An AE **does** include any:

- Exacerbation of a pre-existing illness.
- Increase in frequency or intensity of a pre-existing episodic event or condition.
- Condition detected or diagnosed after study product placement and/or drug administration even though it may have been present prior to the start of the study.
- Continuous persistent disease or symptoms present at baseline that worsen following the start of the study.

An AE **does not** include a/an:

- Medical or surgical procedure (e.g., surgery, endoscopy, tooth extraction, transfusion); the condition that leads to the procedure is an AE.

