7.7.3. Clinical Laboratory Abnormalities and Other Abnormal Assessments as AEs and SAEs

The Investigator should exercise his or her medical and scientific judgment in deciding whether an abnormal laboratory finding, or other abnormal assessment is clinically significant.

Abnormal laboratory findings (e.g., clinical chemistry, hematology, and urinalysis) or other abnormal assessments (e.g., vital signs) that are judged by the Investigator as clinically

significant must be recorded as AEs or SAEs if they meet the definition of an adverse event. Clinically significant abnormal laboratory findings or other abnormal assessments that are detected after study product administration or that are present before study product administration but worsen after study product administration should be assessed for AE criteria.

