8.6. Safety Analyses

Safety analysis will be performed on the safety population. No imputation will be performed for missing data. The incidence (number and percentage of subjects) of adverse events will be presented overall and by MedDRA System Organ Class (SOC) and Preferred Term (PT) for each treatment group. This analysis will be repeated for serious adverse events, for treatment-related adverse events, adverse events of special interest and for adverse events leading to premature study withdrawal.

Descriptive statistics at each time point will be presented for laboratory variables, vital signs, and body weight, stratified by treatment group.

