### 10.3 Adverse Events of Special Interest over 30 Days

- Worsening kidney function, defined as increase of  $\geq 0.5$  mg/dL in serum creatinine
- Hyperkalemia, defined as  $K > 5.5$  mEq/L
- Hypokalemia, defined as  $K < 3.5$  mEq/L
- Hypomagnesemia, defined as  $Mg < 1.5$  mg/dL

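### AESI incidence is a primary endpoint set by four laboratory cut-offs, but the plan tabulates it only by MedDRA term, leaves open whether a crossing alone is recorded, and gives the control arm no denominator

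*SAP*

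**What the plan says.** SAP 10.1 and protocol 3.2.1 list "Incidence of Adverse Events, Adverse Events of Special Interest, and Serious Adverse Events" as a primary endpoint beside the hierarchical composite. Protocol 8.4.1 says what will be done with it: "Incidence of Adverse Events, Adverse Events of Special Interest, and Serious Adverse Events will be described in each group".

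SAP 10.3 and protocol 3.2.3 define the AESIs numerically, over 30 days: "Worsening kidney function, defined as increase of" 0.5 mg/dL or more in serum creatinine, potassium above 5.5 mEq/L, potassium below 3.5 mEq/L, and magnesium below 1.5 mg/dL.

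The planned analysis is term-based. SAP 15.3.3 gives a listing with onset dates and "The number and percentage of subjects with an adverse event of special interest by" MedDRA System Organ Class (SOC) and Preferred Term (PT), for each arm. Protocol 8.6 describes the general AE incidence table by SOC and PT and then says "This analysis will be repeated for serious adverse events, for treatment-related adverse events, adverse events of special interest".

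Three protocol sections bear on recording:
- 6.1.3, on blood drawn at clinic visits, says "Subjects will specifically be monitored for the following adverse events" and lists the four cut-offs.
- 7.1 says "Laboratory or functional test abnormalities generally are not considered AEs unless they are associated with clinical signs or symptoms or require medical intervention".
- 7.7.3 asks the investigator to "exercise his or her medical and scientific judgment in deciding whether an abnormal laboratory finding" matters clinically. It requires recording when the finding is judged significant and meets the AE definition.

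Protocol 8.2 and SAP 14 restrict the Safety population to randomised subjects with one or more doses of investigational product (IP). Protocol 6.2.2 gives controls the same visits without the product.

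**The concern.** A numeric laboratory endpoint and a table of coded terms are different counts. They agree only if every crossing becomes an AE record, and the protocol does not clearly require that. A site that follows 7.1 and 7.7.3 would leave out an asymptomatic crossing that SAP 10.3 defines as an AESI. Because the study is open label, the judgement of significance is made with the arm known, so omissions could differ between arms.

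At stake is a primary endpoint of a study whose primary objective is to supply effectiveness and safety data for a pivotal trial. The Safety definition adds a second problem: an incidence is promised for each group, but one group has no members in the population on which it is to be computed.

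**Working it through.** **Inputs.** Sample size and split: SAP 4. Cut-offs: SAP 10.3. Entry limits: protocol 4.2. Laboratory days 1, 3, 7 and 30: SAP 2. Laboratory analyses: SAP 15.3.4 and 15.2.2. The stated allocation reproduces: 51 × 2/3 = 34 and 51 × 1/3 = 17. The documents give no AESI rate, effect size or power, so there is no AESI figure to reproduce.

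**Step 1: does any planned output count crossings?**
- SAP 15.3.3 and protocol 8.6 count subjects by SOC and PT. Neither names a source dataset or a rule for turning laboratory values into AESIs.
- SAP 15.3.4 gives descriptive statistics, shifts between low, normal and high, and a flag for results more than double the upper reference value or under half the lower one. For the flag to match the AESI cut-offs, the upper potassium limit would have to be 5.5/2 = 2.75, the lower potassium limit 2 × 3.5 = 7.0, and the lower magnesium limit 2 × 1.5 = 3.0. The two potassium limits contradict each other and the eligible range of 3.6 to 5.4. The flag ignores change from baseline, so it cannot find a creatinine rise. The shift categories are not the AESI cut-offs either.
- The creatinine GEE model in SAP 15.2.2 estimates mean change and counts no subjects.
- SAP 7.1 sends unscheduled values to listings only.

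None of these counts subjects who cross a cut-off.

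**Step 2: is a crossing recorded as an AE?** Take a potassium of 3.4 with no symptoms and no intervention. Under SAP 10.3 it is an AESI, and under protocol 6.1.3 an adverse event. Under 7.1 it is generally not one. Under 7.7.3 it must be recorded only if judged significant and if it meets the AE definition. Among up to 20 sites, two could record the same value differently and each point to the protocol.

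**Step 3: can recording differ by arm?** Knowledge of the arm is one route. Another is that 7.1 makes some laboratory abnormalities AEs because they interrupt or stop the IP, which cannot happen in a control. Sections 7.7.3 and 7.7.4 are also worded around product administration. Against this, the Time and Events Schedule assesses AEs at every contact in both arms.

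**Step 4: denominator.** Controls with an IP dose = 0, so the control percentage is 0/0. If a control did receive product, SAP 14 would present that subject by treatment received.

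**Step 5: size.** Assume all 51 randomised subjects are the denominator.
- One subject whose only AESI is unrecorded: 1/34 = 2.9 points (Furoscix) or 1/17 = 5.9 points (control). A missed crossing in a subject with another recorded AESI does not change overall incidence.
- Potassium margin at entry: 3.6 − 3.5 = 0.1 and 5.5 − 5.4 = 0.1. A subject at either entry limit needs a change of just over 0.1 to cross.
- Panels available if complete: 34 × 4 = 136 and 17 × 4 = 68, total 204. These are opportunities to derive the count, not missed events.

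**Illustration with assumed rates, none from the documents.** If 20–30% of Furoscix subjects cross, a laboratory count expects 34 × 0.20 = 6.8 to 34 × 0.30 = 10.2. If 30–60% of those are recorded, the term table expects 34 × 0.20 × 0.30 = 2.0 to 34 × 0.30 × 0.60 = 6.1. With 30% crossing in both arms and recording of 60% (Furoscix) against 30% (control), the table shows 18% against 9%, a 9-point gap where the laboratory difference is 0. Swapping the recording rates reverses the sign, and equal recording gives no gap.

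**The case against.** The strongest reply is that little is missing. The cut-offs and the 30-day window are stated, and SAP 9 defines baseline and change. Only the data source is unstated, and the mock tables cited in SAP 7.1, which are not available here, may settle it. That stands to this extent: reading the SOC/PT table as a count of AE records is an inference, though the most natural one.

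A reader might infer that 6.1.3 and 7.1 flatly contradict each other. The documents do not support that. Section 7.1 says *generally*, and its opening paragraph allows an abnormal laboratory finding as a possible AE, so 6.1.3 can be read as a specific exception. No passage says that it is, so the ambiguity remains. The SAP's own AE definition omits the laboratory exclusion and SAP 15 gives the SAP precedence, but that supplies no derivation and does not tell sites what to record.

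A reader might also infer that under-recording, or a bias towards one arm, is established. It is not. Protocol 7 has AEs assessed continuously and both arms follow the same visits. The dosing-centred wording makes a difference by arm possible, nothing more.

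The Safety-population problem is separate and touches every safety table. That is fair, but an incidence endpoint needs a denominator, and 8.4.1 promises one in each group.

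Finally, the endpoint is descriptive, the study is an unpowered pilot, and the laboratory values are all collected and listed, so the counts can be recovered. All true, and it limits the severity. Without a stated rule, however, the choice between laboratory and term counts could be made after open-label data have been seen.

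**Conclusion.** The point holds as a gap and an unresolved ambiguity, and should be fixed before analysis. Followed as written, the plan can under-count a primary endpoint, because its only AESI table is term-based and the recording rules allow asymptomatic crossings to be left out. The Safety definition also leaves the control arm without a denominator.

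The size of any under-count cannot be computed from the documents. The 2.9 and 5.9 points per subject assume that all randomised subjects are counted by randomised arm, which departs from SAP 14. The 9-point illustration rests wholly on assumed rates.

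A reader might infer that laboratory-derived counts must exceed term-based counts. That is probable but not certain, since an investigator may report an AESI term without a crossing in the study laboratory data.

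**What to change.** In SAP 15.3.3, define the AESI endpoint as the number and percentage of subjects, per arm and per cut-off, derived from scheduled post-baseline laboratory values (Days 1, 3, 7 and 30) at the documents' own cut-offs. Use the Day 0 pre-treatment value as baseline. SAP 9 and 15.2 tie baseline to drug or device start, which controls lack, so name the Day 0 screening value for them.

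Show as supportive:
- the same count with unscheduled values added, as a stated exception to SAP 7.1;
- the investigator-reported AESI terms by SOC and PT.

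Magnesium has no entry limit, so show subjects already below 1.5 mg/dL at baseline separately.

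State that the AESI analysis includes all randomised subjects, controls included, or correct the Safety definition so that it includes controls. In the protocol, reconcile 6.1.3 with 7.1 and 7.7.3 on whether a crossing alone is recorded as an AE.

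The cost is one SAP paragraph, one derived dataset and one protocol clarification, with no new blood draws. Laboratory-derived counts may differ from AE-term counts and will need explaining. Unscheduled sampling is at the investigator's discretion and may differ by arm, which is why that count is only supportive. Unless the Safety definition is corrected, the AESI table will use a different population from the other safety tables.
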